6.2.1 Optional Post-DBPCFC Blood Draw Visit

This visit is only for subjects who consent to participate in the optional post-DBPCFC blood draw for exploratory immune cell characterization by the Immune Tolerance Network (ITN).

The visit is to occur 5-10 days after completion of the Screening DBPCFC and may coincide with an Initial Escalation Day Visit (Section 6.3.1).

The only procedure performed on this day is a blood draw. The amount of blood to be taken for the immune cell characterization assays will be provided in the manual of procedures and will be such that it will not cause the total blood volume collected to exceed 0.67 mL/kg in children, or maximum of 50 mL, total, in 8 weeks. Blood draw should be collected in compliance with local laboratory guidelines and testing regulations.

6.3 Study Treatment Visits

6.3.1 Initial Escalation

6.3.1.1 Initial Escalation, Day-1

The Initial Escalation Day-1 visit should occur within 10 days of the Screening DBPCFC and must occur within 6 weeks from the signing of the informed consent/assent form. If the Initial Escalation is not started in this time frame, written approval to rescreen the subject and/or to waive any of the screening procedures must be obtained from the Sponsor Medical Monitor.

A physician will be available at all times during the CRC peanut OIT dosing visits.

Subjects must be free from active wheezing or a flare of atopic disease (eg, atopic dermatitis), or suspected intercurrent illness prior to initiating study product dose escalation. Additionally, subjects must be fully recovered, ie back to their baseline state of health, from any preceding illness for at least 3 to 7 days, depending on the investigator-determined severity of the illness.

The following assessments/procedures will be performed during the Initial Escalation.

Day-1 visit in the CRC:

- Concomitant medication update
- Physical examination, including weight and height
- Diet (food allergen exposure) history update
- Pre-dose vital sign measurement (blood pressure, pulse rate, body temperature)
- PEFR (3 attempts are to be performed, and the best value taken). PEFR should be measured at the same time for each visit assessment.
- Administration of study product (AR101 or matching placebo), with dosing beginning at 0.5 mg and progressing in graduated doses (if tolerated) of 1, 1.5, 3, and 6 mg. Following the first dose, subsequent doses will be delivered at 20- to 30-minute intervals. The schedule for initial day dose escalation is also shown in Table 3-1.
- Post-dose vital sign measurements (blood pressure, pulse rate) within 15- to 30-minute postdose, and prior to next dose, and at 30 minute intervals thereafter, if the time between doses is extended, and for the duration of the postdose observation period.
- Monitoring for adverse events (AEs), including allergic symptoms (Section 6.7 and Section 7.2)
- Subjects will be reminded to continue to follow a peanut-avoidant diet for the duration of the study.

Subjects may have clear liquids or flavored gelatin (eg, Jell-O) during the day of the initial day escalation procedure while they are being given the desensitization doses.

At a minimum, subjects must be observed for 90 min. $(1\frac{1}{2} \text{ hours})$ after completion of dose escalation, with vital sign measurements and assessment for signs and symptoms of allergic reaction performed every 30 minutes. Any signs or symptoms of allergic reaction will be recorded in the CRF on the appropriate Dosing Symptom/AE form.

If Day-1 dose escalation is completed with no symptoms detected after 1½ hours of post-dose observation, the subject may be sent home from the CRC. If the subject exhibited mild symptoms, the duration of the observation period should be extended to a minimum of 1 hour after resolution of the symptoms. For moderate symptoms, the observation period should be extended to a minimum of 2 hours after resolution of the symptoms. And for severe symptoms, the subject should be observed for a minimum of 3 hours after resolution of the symptoms, either at the CRC or an emergency facility, as appropriate.

Any subject deemed to have severe symptoms that include hypoxia, hypotension, or change in mental status, stage 3 anaphylaxis defined in **Appendix 3**, or who receives intensive therapy (to be determined by the investigator, but may include such interventions as IV epinephrine, intubation, or admission to an intensive care unit) for an allergic reaction at any time should be discussed with the Medical Monitor and discontinued from the study.

If dose-limiting symptoms occur at or before the 3 mg single dose, there will be no further dosing of study product, and the subject will be classified as an escalation failure and a nonresponder for the purpose of primary and key secondary analyses. The subject will be asked to return to the CRC 14 days following the last dose of study product to undergo an Early Discontinuation Visit (Section 6.5). The subject will continue to be monitored for safety until the Early Discontinuation Visit is completed or any ongoing AEs are resolved, whichever is longer.

If no dose-limiting symptoms occur during Day-1 dose escalation, or if dose-limiting symptoms occur only with the 6 mg single dose, the subject is to return to the CRC on Day-2 to confirm the tolerability of a single 3 mg dose of study product.

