Subjects who experience moderate or severe symptoms after receiving the 3 mg dose on Day-2 will be considered escalation failures.

Future dose escalations will occur every 2 weeks with the initial dose increase administered in the clinical research center.

Up-dosing Period Dosing Schedule Study Product Dose Up-dosing (mg peanut protein or Dose # placebo) Interval (weeks) % Increase 1 3 2 2 6 2 100% 3 2 12 100% 4 20 2 67% 5 40 2 100% 6 80 2 100% 7 2 50% 120 8 160 2 33% 9 2 200 25% 10 240 2 20% Enter Maintenance 25% 300 11 Period

Table 3-2.Up-dosing Dosing Schedule for Peanut OIT

Capsules and sachets (introduced during the Maintenance Period) are to be opened, contents sprinkled over an age-appropriate food, and mixed thoroughly. 300 mg capsules will be used for at least the first 2 weeks of dosing during the 24-Week Maintenance Period.

All subjects who reach and tolerate 300 mg/d will continue at that dose level for the duration of the Maintenance Period. The first Maintenance visit occurs 2 weeks after the last Up-Dosing visit, with visits every 4 weeks thereafter. Any subject unable to achieve a dose of 300 mg/d of peanut protein by 40 weeks will be considered an escalation failure nonresponder and will not undergo Exit DBPCFC.

During the treatment period, the subjects will be monitored for the tolerability of study product, as described in Section 6.7.2 and Section 6.7.3, and illustrated in Figure 6-1 and Figure 6-2 (Section 6.7.5.2).

If a subject discontinues therapy prematurely for any reason, the subject will be followed for safety and asked to return to the CRC 14 days following his or her last dose of study product to undergo an Early Discontinuation Visit (Section 6.5). In the event of ongoing AEs, subjects who have discontinued therapy should continue to be followed beyond the Early Discontinuation Visit until such time as the AE has resolved or is assessed to have reached a chronic stable state (a determination that may not be made sooner than 30 days after the Early Discontinuation Visit).

A Data Safety Monitoring Committee (DSMC) will be established and will meet approximately every 3 months to monitor the study for safety.

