Based on experience from Phase 2, most acute allergic responses to dosing that are characterized by mild symptoms would be anticipated to meet the above criteria. If, however, an allergic response to dosing is characterized by mild symptoms that do not meet all of the above criteria (eg, has mild symptoms occurring in 2 or more organ systems, requires treatment with 2 doses of antihistamine or 1 dose epinephrine, shows progression in severity or distribution over time, is protracted in duration, or includes objective wheezing), then even though the allergic symptoms may be mild, the dose should be assessed to be not tolerated. If a dose elicits mild symptoms that do not fit all of the above criteria and the dose is assessed to be tolerated, then a brief explanation as to why the dose was considered tolerated must be recorded in the CRF.

Moderate symptoms: In general, if a dose elicits moderate symptoms, the dose will be assessed as not tolerated. There may, however, be rare occasions when a dose eliciting moderate symptoms could be assessed as tolerated. Generally, this would only be the case for a transient, self-limited (requiring no intervention and resolving completely) symptom occurring in a single organ system. In addition, typically the symptom would be subjective only. Any dose associated with moderate symptoms and assessed as tolerated must be accompanied by a brief explanation in the CRF as to why the dose was considered tolerated.

Severe symptoms: In nearly all cases, if a dose elicits severe symptoms, the dose will be assessed as not tolerated. Whenever a dose elicits an allergic response characterized by 1 or more severe symptoms, the crucial decision, after adequate treatment for the allergic reaction has been administered, will be to determine whether the subject should continue in the study, dosing at a reduced dose level, or be discontinued early from the study.

The determination of tolerability will decide the course of action to be taken in response to doserelated reactions (Section 6.7.3).

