6.7.4 Treatment of Acute Reactions to Peanut OIT during Initial Escalation

The process algorithm for responding to acute allergic symptoms during OIT is shown in **Figure 6-1** in **Section 6.7.5**.

Investigator judgment will be required to determine the best course of action, with possible actions being the following:

- Extending the time interval between dosing (up to an additional 30 min) without any additional treatment
- Instituting enhanced clinical monitoring. This could include (though is not limited to) more frequent vital sign monitoring (including respiratory rate), auscultation, and/or the addition of pulse oximetry
- Treating with antihistamine and then resuming dose escalation within 60 minutes of last dose, if assessed as safe
- Treating additionally with epinephrine, beta-agonist, oxygen, IV fluids, and/or glucocorticosteroids, as necessary, and discontinuing dose-escalation
- Discontinuation of desensitization protocol

Mild symptoms: For *oral/pharyngeal pruritus* occurring in isolation, a specific type and commonly occurring mild allergic reaction, the recommended action is to advance to the next dose in 30 min (though the action taken is, as always, at the investigator's clinical discretion).

For other *mild symptoms*, the action to be taken, at the investigator's discretion, should be to either:

- Advance to next dose in 30 to 60 minutes or
- Treat with antihistamine and then resume dose escalation within 60 minutes of last dose, provided that symptoms have resolved to the point where the investigator assesses the subject to be safe to continue dosing (ie, having no or only minimal residual signs or symptoms)

In general, if a subject requires only 1 or two doses of antihistamine to treat mild symptoms occurring during the course of the initial escalation, then the initial escalation may continue. If, however, the subject requires a second medication (eg, epinephrine or a beta-agonist) to treat the symptoms, or more than 2 doses of an antihistamine, the initial escalation is to be terminated and the subject is to receive no further OIT, even if the symptoms were assessed to be mild. Use of epinephrine to treat dose-related symptoms, even in the unlikely event that the symptoms are graded as mild, will be cause to terminate the initial escalation.

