Moderate symptoms: For *moderate symptoms*, if the symptoms are not worsening or amassing at a rapid pace, then a stepwise approach to treatment may be taken at the discretion of the investigator. If the first action undertaken is to implement an observation period, the observation period should not exceed 30 min before either the symptoms are noted to be resolving or therapy is instituted. Whether treatment is initiated immediately or after an observation period, the subject may be treated first with antihistamines or immediately with epinephrine, as deemed appropriate by the investigator. Other therapies may be added either sequentially or simultaneously, per investigator judgment.

If moderate symptoms occur at any of the doses below 6 mg (ie, up to and including 3 mg), then the desensitization procedure will be discontinued and the subject considered an escalation failure and desensitization nonresponder. The decision to discontinue escalation is to be based solely on the determination of whether the allergic reaction was of moderate severity. Although it is generally the case that some form of treatment will be instituted for moderate symptoms, treatment is not a requirement for assessing an allergic reaction as being of moderate severity.

Severe symptoms: For *severe symptoms*, the actions taken should be to discontinue the initial escalation and administer the appropriate rescue medications. The desensitization procedure will be discontinued regardless of the dose at which the severe symptom or symptoms occurred, and the subject will be considered an escalation failure and desensitization nonresponder.

A Medical Monitor (from INC or Aimmune) is to be available at all times to answer any questions or to assist in any decisions related to the study protocol.

[figure not shown]

Figure 6-1: Schematic for Initial Escalation Day-1

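### A severe reaction confined to the 6 mg Day-1 dose is given two opposite dispositions (return for Day-2 dosing, or discontinuation as a nonresponder), with a rarer conflict of the same kind for moderate reactions assessed as tolerated

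*Protocol*

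**What the plan says.** The protocol describes initial escalation in two places, on two scales.

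**Visit procedures (6.3.1.1 and 6.3.1.2): dose-limiting symptoms, or tolerability.**
- Day-1, up to 3 mg: "If dose-limiting symptoms occur at or before the 3 mg single dose, there will be no further dosing of study product", and the subject is an escalation failure and nonresponder.
- Day-1, 6 mg: "if dose-limiting symptoms occur only with the 6 mg single dose, the subject is to return to the CRC on Day-2" to confirm a single 3 mg dose. A separate paragraph discontinues severe reactions with hypoxia, hypotension or mental-status change, stage 3 anaphylaxis, or intensive therapy.
- Day-2: dose-limiting symptoms mean failure. A tolerated 3 mg dose means that a two-week home supply is dispensed.

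The Synopsis (Initial Escalation) and the Day-1 notes to protocol Table 3-1 and SAP Table 2.2 likewise bring back a subject who tolerated 3 mg, with no severity limit at 6 mg.

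**Treatment of reactions (6.7.4): severity grade.**
- Moderate symptoms at doses up to 3 mg end the procedure: "The decision to discontinue escalation is to be based solely on the determination of whether the allergic reaction was of moderate severity".
- Severe symptoms: "The desensitization procedure will be discontinued regardless of the dose at which the severe symptom or symptoms occurred", with classification as escalation failure and nonresponder.

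The Day-2 note to Table 3-1, repeated in the Synopsis and in SAP Table 2.2, is also severity-based: "Subjects who experience moderate or severe symptoms after receiving the 3 mg dose on Day-2 will be considered escalation failures".

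**Related text.** Section 4.3.1 puts severe (CoFAR Grade 3) symptoms among the reasons for which a subject will be terminated from further allergen exposure. Section 6.7.2 separates severity from tolerability: "There may, however, be rare occasions when a dose eliciting moderate symptoms could be assessed as tolerated".

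**The concern.** Severity and tolerability usually agree, so two scales would do little harm if each section gave the same answer where they part. In two situations they do not. The more serious is a severe reaction that appears only at 6 mg: one section schedules another dose of study product, and another section treats the same reaction as terminal. At least 80% of randomized subjects are children.

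The endpoint is touched as well. A subject stopped in initial escalation has no Exit challenge and counts as a nonresponder (protocol 9.2.1; SAP 7.4.2). A subject who goes on may reach the Exit challenge and be a responder (SAP 7.4.1). The section that a site follows therefore helps to decide who has the chance to respond.

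**Working it through.** No formula applies and the plan gives no figure to reproduce. The check is to trace each reaction through both sets of rules. Reactions whose disposition turns on rescue medication are outside this point.

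**Step 1: is dose-limiting the same as not tolerated?** Section 6.6 says that dose-limiting symptoms in a food challenge are judged by the tolerability criteria of 6.7, with one exception for treated mild symptoms. I read 6.3.1 the same way. Under 6.7.2, severe symptoms are nearly always not tolerated, and moderate symptoms usually are not.

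**Step 2: compare the outcomes.**

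| Reaction | 6.3.1.1 / 6.3.1.2 | 6.7.4 and related text | Result |
|---|---|---|---|
| Severe, at or below 3 mg | Stop, failure | Stop, failure | Agree |
| Severe, 6 mg only, within the 6.3.1.1 exception | Discontinue | Discontinue | Agree |
| Severe, 6 mg only, outside the exception | Return on Day-2 for 3 mg | Discontinue, failure; 4.3.1 terminates | **Conflict** |
| Moderate, at or below 3 mg, not tolerated | Stop, failure | Stop, failure | Agree |
| Moderate, at or below 3 mg on Day-1, assessed as tolerated | Continue | Stop, failure | **Conflict (rare)** |
| Moderate, 3 mg on Day-2, assessed as tolerated | Dispense home supply | Failure (6.7.4 and Day-2 notes) | **Conflict (rare)** |
| Moderate, 6 mg | Return on Day-2 | Failure rule covers only doses below 6 mg | No conflict |

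**Step 3: can the third row occur?** Yes. Section 6.7.1 grades as severe, among others, severe generalized urticaria or angioedema, stridor, wheezing with dyspnea, and repetitive vomiting. None of these need bring hypoxia, hypotension, mental-status change or intensive therapy. Appendix 3 places stridor at stage 2, so a reaction that is severe under 6.7.1 need not be stage 3 anaphylaxis.

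**Step 4: does other text settle it?** Section 4.3.1 points the same way as 6.7.4 but does not qualify the 6 mg sentence. The severe-symptom paragraph of 6.7.2 points elsewhere again: it leaves continuing at a reduced dose level as a decision to be made. I find no statement of which section governs. Figure 6-1, the Day-1 schematic, is not shown in the text available and could not be checked.

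**The case against.** The best defense is that this is one under-qualified sentence. Two explicit provisions, 6.7.4 and 4.3.1, stop a subject with severe symptoms, and a Medical Monitor is available at all times. That lowers the chance of a bad outcome. It does not remove the contradiction, because the sentence sits in the visit procedures and its rule is repeated in the Synopsis and in SAP Table 2.2.

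For moderate symptoms the defense is stronger. Section 6.7.4 is specific to initial escalation and bases the decision on severity alone, and the Day-2 notes allow home dosing only after no symptoms or mild, non-dose-limiting ones. Most readers would follow the specific rule. What remains is narrow and depends on an assessment that 6.7.2 itself calls rare.

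Enrolment was complete by Amendment 4 (protocol 9.4), and initial escalation is the first two treatment days, so little or no ARC003 dosing is likely to change. That stands. But protocol 3.4 has former placebo subjects escalate in ARC004 by the same schedule and procedures, on active product.

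Two stronger readings are tempting, and the documents do not support them.
- *Mild symptoms as a third conflict.* Section 6.7.2 gives a reaction that "has mild symptoms occurring in 2 or more organ systems" as an example of a dose to be assessed as not tolerated, while 6.7.4 offers "Advance to next dose in 30 to 60 minutes". Both are discretionary. The 6.7.2 criteria are guidelines, from which an investigator may depart with an explanation in the CRF. The 6.7.4 step is one option at the investigator's discretion, and stopping is among the actions listed there. These are not opposite dispositions.
- *Ambiguous responder classification in the analysis.* SAP 7.4.1 and 7.4.2 classify by the Exit challenge, and SAP Table 7.1 assigns escalation failure by the period of the last dose. Once a subject's course is known, the classification follows. The conflict acts earlier, on the course itself.

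**Conclusion.** The point holds for two reactions. A severe reaction only at 6 mg, outside the 6.3.1.1 exception, is sent back for Day-2 dosing by one section and discontinued as a nonresponder by another. A moderate reaction at or below 3 mg that is assessed as tolerated is allowed on by 6.3.1 and failed by 6.7.4 and the Day-2 notes; this second conflict is narrow and rare. The first bears on safety, and both bear on who can reach the Exit challenge.

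The size cannot be computed, because neither document gives a frequency for either reaction. A reader might infer a loss of power by assuming that some share of AR101 children is failed under the stricter section. No such share can be drawn from the documents. The assumed 50% AR101 response was also already set below the Phase 2 point estimates of 62% to 79%, with dropout cited as a reason (protocol 9.4), so a further deduction from it has no clear basis.

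The conclusion rests on reading dose-limiting as not tolerated, and on Figure 6-1 not already resolving the matter.

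**What to change.** Reconcile the Synopsis (Initial Escalation and its table notes), the Table 3-1 notes in 3.2, and sections 4.3.1, 6.3.1.1, 6.3.1.2, 6.7.2 and 6.7.4 of the protocol, together with SAP Table 2.2, and check Figure 6-1 against the result. State one disposition for each of:

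1. severe symptoms occurring only at 6 mg on Day-1, outside the present 6.3.1.1 exception;
2. moderate symptoms at or below 3 mg, on Day-1 or Day-2, that the investigator assesses as tolerated.

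The sponsor chooses the rule; this review takes no position on which is right.

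At the blinded review already planned before database lock (SAP section 11), list any subjects with either reaction and record how each was handled. Check whether the same text has carried into ARC004 and align it if so.

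The cost is a protocol clarification, a matching SAP table note and one listing at blinded review. It adds no visits or subjects and leaves the statistical methods unchanged.

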6.3.1.2 Initial Escalation, Day -2

On Day -2, a single confirmatory 3 mg dose will be administered under medical supervision in the CRC.

Subjects must be free from active wheezing, a flare of atopic disease (eg, atopic dermatitis), or suspected intercurrent illness prior to continuing with Day -2 of the initial dose escalation. Consistent with the rules for missed doses (Section 6.8), Day -2 dosing may not be postponed for more than 2 weeks.

The following assessments/procedures will be performed during the Initial Escalation

Day -2 visit in the CRC:

- Symptom-directed physical examination
- Pre-dose vital sign measurement (blood pressure, pulse rate, body temperature)
- PEFR (3 attempts are to be performed, and the best value taken). PEFR should, as far as possible, be measured at the same time for each visit assessment.
- Oral administration of a single 3 mg dose of study product
- Post-dose vital sign measurements (blood pressure, pulse rate) within 15 to 30 minutes postdose, and at 15- to 30- minute intervals thereafter for the postdose observation period
- Monitoring for adverse events (AEs), including allergic symptoms (Section 6.7)
- Subjects will be reminded to continue to follow a peanut-avoidant diet for the duration of the study.

At a minimum, subjects must be observed for 1½ hours after dose administration, with vital sign measurements and assessment for signs and symptoms of allergic reaction performed every

30 minutes. Any signs or symptoms of allergic reaction will be recorded in the CRF on the appropriate Dosing Symptom / AE form.

If Day -2 dosing is completed with no symptoms detected after 1½ hours of post-dose observation, the subject may be sent home from the CRC. If the subject exhibited mild symptoms, the duration of the observation period should be extended to a minimum of 1 hour after resolution of the symptoms. For moderate symptoms, the observation period should be extended to a minimum of 2 hours after resolution of the symptoms. And for severe symptoms, the subject should be observed for a minimum of 3 hours after resolution of the symptoms, either at the CRC or an emergency facility, as appropriate.

Any subject deemed to have severe symptoms that include hypoxia, hypotension, or change in mental status (stage 3 anaphylaxis defined in **Appendix 3**), or who receives intensive therapy (to be determined by the investigator, but may include such interventions as IV epinephrine, intubation, or admission to an intensive care unit) for an allergic reaction at any time should be discussed with the Medical Monitor and discontinued from the study.

If dose-limiting symptoms occur on Day -2, there will be no further dosing of study product, and the subject will be classified as an escalation failure and a nonresponder for the purpose of primary and key secondary analyses. The subject will be asked to return to the CRC 14 days following the last dose of study product to undergo an Early Discontinuation Visit (Section 6.5). The subject will continue to be monitored for safety until the Early Discontinuation Visit is completed or any ongoing AEs are resolved, whichever is longer.

Those subjects who tolerate the single 3 mg dose of study product on Day -2 will be dispensed a 2-week supply of study product at the 3 mg/d dose level. They will be instructed to continue daily oral dosing at home, starting the following day (Study Day -3), and to continue daily home dosing at that dose level for 2 weeks until next escalation.

On Day -3, the site is to make telephone contact with the subject/subject's parent or guardian to enquire if any AEs (including allergic symptoms) occurred subsequent to the subject leaving the clinic, and to provide assistance in recording of, and responding to, any such events.

